Specimens will be collected according to the schedule in Section 6. Specimens will be collected after subject eligibility confirmation, but prior to administration of the first dose of nintedanib and subsequent cycles. Exploratory biomarker arrays may be used.

Radiology and Tumor Measurements. A computed tomography (CT) scan with oral and intravenous contrast of the chest, abdomen and pelvis will be performed within 28 days prior to the first dose of nintedanib (screening scan). Scans will then be performed within 7 days following anticipated completion of cycle 2 unless clinically proven otherwise and within 7 days of anticipated completion of every two cycles thereafter (e.g. end of cycles 4, 6). A contrast-enhanced MRI of the abdomen and pelvis and a CT scan of the chest without contrast may be substituted if clinically necessary; however, subsequent studies must be performed using the same imaging modality throughout the study period.

For subjects who discontinue study therapy due to toxicity or reasons other than progressive disease, every effort will be made to obtain imaging studies and tumor assessments every 8 weeks (+/- 2 weeks) until documented progression or the start of subsequent anti-cancer therapy.

Subsequent Therapy and Survival Status. Once subjects complete their End of Treatment visit, they will be followed until all treatment-related toxicities have resolved, returned to baseline, stabilized, or are deemed irreversible. Subject's initial anti-cancer therapy following discontinuation of nintedanib treatment and survival

status will be documented.

Subjects (or their family members or designees) may be contacted by telephone, in writing, or during clinic visits after treatment discontinuation for collection of long-term follow-up data approximately every 6 months until death or lost to follow-up, or until the criteria defined for the final analysis (Section 13.3.1) are reached. However, in the event the criteria for the final analysis are met, and there are subjects who have not yet been discontinued from nintedanib treatment, subjects in follow up will continue to be followed until all subjects have discontinued study treatment and completed the safety monitoring period. Long-term follow-up clinical information may also be obtained through chart reviews.

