6. STUDY CALENDAR

Cycle = 28 days (no visit on Week 4)

	Pre-treatment	Clinical Study Treatment						Post-treatment		
	Screening Within 28 days (prior to Cycle 1)	Cycle 1 (+/- 3 days)			Cycle 2 (+/- 3 days)			Remaining Cycles (+/- 3 days)	End of Treatment	Follow-up
Week		W1	W2	W3	W1	W2	W3	W1	Within 30 days of last drug dose	Every 6 months until death , LTF, or completion of long- term follow-up
Informed consent and HIPAA waiver	X									
Demographics	X									
Medical history	X									
Urine or serum pregnancy test ^a	X									
Concurrent medications ^m	X	X			X			X	X	
Physical exam ^{g,m}	X	X ^e			X			X	X	
Vitals ^{h,m}	X	X	X ⁿ	X ⁿ	X	X ⁿ	X ⁿ	X	X	
ECOG performance status ^m	X	X ^e			X			X	X	
Adverse event evaluation ^o	X	Ongoing							X	
CBC w/differential ^m	X	X ^e			X			X	X	
CMP ^{j,m}	X	X ^e			X			X	X	
PTT	X									
PT/INR	X	X ^e								
Urinalysis	X									

Serum for correlative studies ^{b,m}		X			X			X	X	
Ascites for correlative studies ^k		X	X	X	X	X	X	X	X	
Radiologic evaluation by CT and tumor measurements by RECIST 1.1	X						X ^c	X ^d	X	X ^f
Survival status										X ^l
Nintedanib dispensing ⁱ		X			X			X		
Nintedanib compliance assessment					X			X	X	

- a: In women of child-bearing potential; within 7 days of study drug administration and as clinically indicated throughout participation in the study
- b: Serum sample will be collected and assayed for VEGF levels and stored for future study. At the C1D1 timepoint, collect serum after subject eligibility confirmation but prior to first nintedanib dose. At all time-points, serum should be collected prior to nintedanib dosing.
- c: Within 7 days of anticipated completion of cycle 2
- d: Within 7 days of anticipated completion of every two cycles) (e.g. cycles 4, 6, 8)
- e: Not required if screening procedure done w/in 7 days of C1D1 per section 5.5
- f: For subjects with disease control and who discontinue study therapy due to toxicity or reasons other than progressive disease, every effort will be made to obtain imaging studies and tumor assessments every 8 weeks (+/- 2 weeks) until documented progression or the start of new anti-cancer therapy
- g: Physical exam: includes height (at screening only); Weight; body surface area (BSA).
- h: Vitals: temperature; pulse rate; respiratory rate; blood pressure, oxygen saturation

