7. TREATMENT PLAN

7.1. Nintedanib Dosage and Administration

Research participants for this study will initiate treatment with 200mg of oral nintedanib twice per day. The capsules should be swallowed whole (unopened, uncrushed) with a glass of approximately 8 oz. /240 mL of water. Since subjects will be taking oral nintedanib twice daily, the dose interval should be every 12 hours at the same time every day, usually in the morning and the evening after food intake.

In case of a missed dose the subjects should not replace that dose, but proceed to the next scheduled dose when it is due. Each study cycle length is 28 days.

In the event of a treatment delay at the scheduled Day 1 of a cycle, Day 1 of that cycle will be delayed until study treatment is re-started. This may cause a cycle to extend to longer than 28 days. Day 1 will be defined as the day the treatment is re-started.

For dose selection and modifications, see Section 8.

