8.2. Criteria to Restart Treatment with Nintedanib

A research participant is eligible to restart nintedanib if all criteria listed in Table 2 are met.

If a subject must interrupt intake of nintedanib due to an adverse event for more than 14 days, the decision to restart treatment with nintedanib needs to be discussed and agreed upon between the sponsor-investigator and the treating physician.

Table 2: Criteria to assess eligibility to restart nintedanib treatment

All criteria must be met in order to restart nintedanib, meaning AEs have to return to Grade 1 or baseline (exception is nausea- see below).
 
  nausea CTCAE grade ≤ 2  vomiting CTCAE grade ≤ 1  diarrhea CTCAE grade ≤ 1  AST and ALT $< 2.5 \times \text{ULN}$; bilirubin $< 1.5 \times \text{ULN}$  no other non-hematological adverse event grade CTCAE ≥ 3 which is considered drug-related  *Neutropenia CTCAE grade ≤ 1, without fever or equal to the subject's pre-therapy value at study enrolment  *Platelets CTCAE grade ≤ 1 or equal to the subject's pre-therapy value at study enrolment  Blood pressure SBP<150 mm Hg; DBP <90 mm Hg  Bleeding CTCAE grade 1 or less
--

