13.1.4. Six-Month Progression-Free Survival

Six-month progression-free survival will be determined for each subject as a binary variable indicating whether or not the subject is alive and progression free at 6 months. The criteria for a PFS event are defined in Section 13.1.3.

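### On-treatment scan dates are not fixed once a cycle is delayed, so the scan that decides 6-month PFS can fall after 6 months

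*Combined protocol and SAP*

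**What the plan says.** **Scan timing.** Section 5.5 sets the first on-treatment scan thus: "Scans will then be performed within 7 days following anticipated completion of cycle 2". Later scans are due "within 7 days of anticipated completion of every two cycles thereafter". Footnotes c and d of the Study Calendar (Section 6) use the same anchor. Section 5.2 mixes units, placing the first evaluation after two months and later ones every two cycles. After discontinuation for a reason other than progression, Section 5.5 asks for scans every 8 weeks, plus or minus 2 weeks.

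**Cycle length.** A cycle is nominally 28 days. When treatment is delayed at a scheduled Day 1, Section 7.1 says "Day 1 of that cycle will be delayed until study treatment is re-started", and adds: "This may cause a cycle to extend to longer than 28 days". Section 8.1 repeats this. Neither gives a maximum. Section 8.2 foresees interruptions of more than 14 days and requires the sponsor-investigator and treating physician to agree before a restart.

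**Endpoints.** Section 13.1.3 dates objective progression at the scan that shows it, investigator-determined progression at the clinician's decision, and death at its own date. Section 13.1.4 defines 6-month PFS as a yes/no variable: "whether or not the subject is alive and progression free at 6 months". It gives neither a definition of 6 months in days nor an assessment window. Section 13.3.4.2 reports the rate with a 95% Clopper-Pearson interval and no test.

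**The concern.** Once a Day 1 has moved, the due date of the next scan is unclear. The word *anticipated* could mean the date first planned or the date expected after the delay, and no section settles it. On the second reading, scan timing depends on toxicity. A subject held at a Day 1 is scanned later, and objective progression is dated later. If the cycle 6 scan slips past 6 months, that subject's 6-month status rests on the cycle 4 scan.

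Three features make this worth settling:

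- The trial has a single arm, so no control group shares the same distortion.
- Section 13.3.4.2 considers nintedanib exposure as a covariate. Delays lower exposure and may also postpone scans, which could create an artificial link between lower exposure and longer PFS.
- Section 13.1.3 censors events that follow two or more consecutive missed assessments. Counting missed assessments requires a clear due date.

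**Working it through.** **1. The plan's own figures.** The documents give no design figure for 6-month PFS. For disease control, Section 13.1 states one-sided alpha 0.10 and at least 90% power, with continuation at 8 or more of 28 and rejection at 16 or more of 39. The exact probability of rejection is the sum over x = 8 to 28 of P(X1 = x) × P(X2 ≥ 16 − x), with X1 ~ Bin(28, p) and X2 ~ Bin(11, p).

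- p = 0.30: 0.0943
- p = 0.50: 0.9001

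Both reproduce the stated figures. Scan dates do not enter this calculation.

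**2. Dates.** Inputs: 28-day cycles, and a window of plus or minus 7 days for the later scans (my reading of Section 5.5 and footnote d). Six months is taken as 365.25 / 2 = 182.6 days, about day 183 (assumed).

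- Cycle 6 scan with no delay: 6 × 28 = day 168, window 161 to 175. This is before 6 months even at its latest.
- Room before the landmark: 182.6 − 168 = 14.6 days for an on-time scan, 182.6 − 175 = 7.6 at the late edge, and 182.6 − 161 = 21.6 at the early edge.
- A cumulative Day 1 delay of about 15 days (8 to 22 across the window) therefore puts the scan after 6 months. With 6 months taken as 180 to 184 days, the on-time room is 12 to 16 days.

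**3. Effect on one subject.** Assume exponential PFS with a median of 120 days, so S(d) = 2^(−d/120), and progression found only at scans. The subject is counted progression-free at 6 months if the last scan before the landmark is clear.

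| Day 1 delay | Last scan before 6 months | S(d) |
|---|---|---|
| None | day 168 | 0.379 |
| 15 days or more, all after the cycle 4 scan | day 112 | 0.524 |
| 15 days, before the cycle 4 scan | day 127 | 0.480 |
| 28 days, before the cycle 4 scan | day 140 | 0.445 |
| 42 days, before the cycle 4 scan | day 154 | 0.411 |

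For delays of 15 to 28 days the chance is about 44% to 52%, against 38%. The excess shrinks for longer early delays because the cycle 4 scan also moves later.

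**4. Other medians.** For a 15-day delay before the cycle 4 scan (months of 30.4 days):

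| Median PFS | Delayed | Not delayed | Difference |
|---|---|---|---|
| 2 months | 0.235 | 0.148 | 0.087 |
| 3 months | 0.381 | 0.279 | 0.102 |
| 4 months | 0.485 | 0.384 | 0.101 |
| 6 months | 0.618 | 0.529 | 0.089 |

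**5. Effect on the cohort.** The documents do not say how many subjects will be delayed, so assume 10% to 40%. The rise in the rate is the fraction delayed times the difference.

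- Low end: 0.10 × 0.087 = 0.9 points, or 39 × 0.0087 = 0.3 subjects.
- High end: 0.40 × 0.102 = 4.1 points, or 39 × 0.0408 = 1.6 subjects.

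**The case against.** The strongest reply is that *anticipated* completion already means the planned date, so scans never move; Section 5.2's reference to two months points the same way. That reading is possible. But Section 7.1 redefines Day 1 as the restart date, and nothing keeps scans on the original dates. Two sites could follow the text faithfully and scan on different days.

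A reader might infer that any 15 days of held treatment push the scan past 6 months. The text does not support this. Only a delay at a scheduled Day 1 moves the cycle. A hold that starts and ends mid-cycle is not said to extend anything, and only days beyond the scheduled Day 1 count. Such delays are nevertheless plausible: the metabolic panel is drawn in Week 1 of each cycle, Section 2.2.2 names liver-enzyme elevation as the main dose-limiting toxicity, and Table 1 lists it as a reason to interrupt.

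Two further points stand. Investigator-determined progression and deaths are dated between scans, so the figures above are upper-end illustrations. A delay below the threshold does not inflate 6-month PFS. At a 4-month median, a 14-day delay gives 0.355, against 0.384 with no delay, because the scan moves closer to the landmark.

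It would also be wrong to say that scan intervals differ in general between on-treatment and off-treatment subjects. Two 28-day cycles are 8 weeks; without a delay only the window differs.

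**Conclusion.** The plan leaves the on-treatment scan date undefined after a Day 1 delay. If scans follow the delayed cycles, objective progression is dated later in those subjects, and a cumulative delay of about 15 days (8 to 22 with the window) removes the cycle 6 scan from the 6-month assessment. The sizes shown rest on an assumed exponential PFS, assumed medians, detection only at scans and an assumed share of delayed subjects. They indicate a modest upward shift, not an established bias.

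A reader might infer that the primary result is compromised. The documents do not support that: 6-month PFS is secondary, has no hypothesis test or decision rule, and the stated type I error and power for disease control do not change. The point is a worthwhile correction, not a threat to the trial's main conclusion.

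**What to change.** In Sections 5.2 and 5.5 and in calendar footnotes c and d, schedule on-treatment scans at weeks 8, 16 and 24 and every 8 weeks after that, counted from Cycle 1 Day 1, with the same 7-day window. State that dose delays do not move them and that they continue until progression or new anti-cancer therapy. The third scan then falls on day 161 to 175 for everyone, before 6 months, and the nominal interval matches the off-treatment one.

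Section 13.1.4 should also define 6 months in days and say how status is read, because no scheduled scan falls on the landmark itself.

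The cost is small: essentially the same scans on fixed dates, with no change to any dosing rule. Some scans will not coincide with a Day 1 visit. Under Table 5 in Section 11.4.4, the change needs the funding company's prior approval and, if classed as major, the IRB's prior approval; if minor, the IRB is notified within 90 days.

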6. STUDY CALENDAR

Cycle = 28 days (no visit on Week 4)

	Pre-treatment	Clinical Study Treatment						Post-treatment		
	Screening Within 28 days (prior to Cycle 1)	Cycle 1 (+/- 3 days)			Cycle 2 (+/- 3 days)			Remaining Cycles (+/- 3 days)	End of Treatment	Follow-up
Week		W1	W2	W3	W1	W2	W3	W1	Within 30 days of last drug dose	Every 6 months until death , LTF, or completion of long- term follow-up
Informed consent and HIPAA waiver	X									
Demographics	X									
Medical history	X									
Urine or serum pregnancy test ^a	X									
Concurrent medications ^m	X	X			X			X	X	
Physical exam ^{g,m}	X	X ^e			X			X	X	
Vitals ^{h,m}	X	X	X ⁿ	X ⁿ	X	X ⁿ	X ⁿ	X	X	
ECOG performance status ^m	X	X ^e			X			X	X	
Adverse event evaluation ^o	X	Ongoing							X	
CBC w/differential ^m	X	X ^e			X			X	X	
CMP ^{j,m}	X	X ^e			X			X	X	
PTT	X									
PT/INR	X	X ^e								
Urinalysis	X									

Serum for correlative studies ^{b,m}		X			X			X	X	
Ascites for correlative studies ^k		X	X	X	X	X	X	X	X	
Radiologic evaluation by CT and tumor measurements by RECIST 1.1	X						X ^c	X ^d	X	X ^f
Survival status										X ^l
Nintedanib dispensing ⁱ		X			X			X		
Nintedanib compliance assessment					X			X	X	

- a: In women of child-bearing potential; within 7 days of study drug administration and as clinically indicated throughout participation in the study
- b: Serum sample will be collected and assayed for VEGF levels and stored for future study. At the C1D1 timepoint, collect serum after subject eligibility confirmation but prior to first nintedanib dose. At all time-points, serum should be collected prior to nintedanib dosing.
- c: Within 7 days of anticipated completion of cycle 2
- d: Within 7 days of anticipated completion of every two cycles) (e.g. cycles 4, 6, 8)
- e: Not required if screening procedure done w/in 7 days of C1D1 per section 5.5
- f: For subjects with disease control and who discontinue study therapy due to toxicity or reasons other than progressive disease, every effort will be made to obtain imaging studies and tumor assessments every 8 weeks (+/- 2 weeks) until documented progression or the start of new anti-cancer therapy
- g: Physical exam: includes height (at screening only); Weight; body surface area (BSA).
- h: Vitals: temperature; pulse rate; respiratory rate; blood pressure, oxygen saturation
- i: Nintedanib capsules should be swallowed whole (unopened, uncrushed) with a glass of approximately .8 oz. /240 mL of water. Since subjects will be taking oral nintedanib twice daily, the dose interval should be every 12 hours at the same time every day, usually in the morning and the evening after food intake.
- j: Direct bilirubin required if total bilirubin above normal
- k: Ascites fluid to be collected and assayed for VEGF levels and stored for future study. The decision to remove ascites fluid by paracentesis is determined **as clinically indicated by the investigator** based on subject symptoms. If paracentesis is done as part of standard of care, then every attempt will be made to collect a portion of ascites fluid and store for possible future study
- l: Subject's initial anti-cancer therapy following discontinuation of nintedanib treatment and survival status will be documented.
- m. May be performed within 72 hours of Day 1 of each cycle unless otherwise noted
- n Blood pressure (only) will be assessed on Day 8 and Day 15 (+/- 2 days) during the first 2 cycles of study treatment. Blood pressure assessment may be done at home by the subject or at another clinic (i.e. local pharmacy), and the research staff will be responsible for obtaining these results from the subject. Phone contact is acceptable.
- o. AE evaluation should be performed on Day 8 and Day 15 (+/- 2 days) of Cycles 1 and 2 when the research staff is contacting the subject for BP results.

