11.4. Adverse Event and Deviation Reporting

11.4.1. Reporting to the Sponsor (LCI)

All adverse events from the time of study treatment initiation until 30 days after last dose of study drug (including event name, grade, start/stop date and attribution) will be documented in the medical record and/or research chart and recorded on the case report form for this protocol.

The investigator is responsible for verifying and providing source documentation for all adverse events and assigning the attribution for each event for all subjects enrolled on the trial.

Protocol-specified AESI are to be reported in an expedited manner similar to Serious Adverse Events, even if they do not meet any of the seriousness criteria.

SAEs and AESIs must be reported to the Sponsor-Investigator within 24 hours of awareness via the CTMS.

Information not available at the time of the initial report which is received after the initial report must be documented on a follow-up SAE utilizing the same process described above for reporting the initial SAE/AESI. For expedited reporting involving drug exposure during pregnancy, a follow-up report to describe the outcome of the pregnancy is required within 24 hours of investigator awareness.

SAEs will be captured from the time of signing of the informed consent through 30 days after the date of the last study drug administration. SAEs and AESIs will be followed until clinical recovery is complete, laboratory tests have returned to baseline, or until there has been acceptable resolution of the event. This may at times cause the follow-up period for SAEs and AESIs to be greater than 30 days. The above referenced 30-day time period applies even if the subject is taken off treatment and initiates subsequent anti-cancer treatment during this time period. Similarly, the treating investigator is responsible for following the subject during the required follow-up period even if the subject lives elsewhere or has been released from his or her care.

Deviations from the investigational plan must be reported to the sponsor via entry into the CTMS as soon as they occur, but within no more than 10 business days of becoming aware of the event (as soon as possible for deviations reportable to the IRB).

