11.4.3. Safety Reporting to Funding Company (Boehringer Ingelheim Pharmaceuticals Inc.)

During the conduct of the study the Sponsor-Investigator shall report all

- i. SAEs,
- ii. AESIs independent of their seriousness,
- iii. and non-serious AEs which are relevant to a reported SAE or AESI
- iv. Pregnancies

by fax or other secure method using BI IIS SAE form providing as much detail as possible (pregnancies using Pregnancy Monitoring Form) to the BI Unique Entry Point in accordance with the timelines specified below as per the Pharmacovigilance agreement.

- within five (5) calendar days of the Sponsor-Investigator's knowledge of initial and follow-up SAEs containing at least one (1) fatal or immediately life-threatening event;
- within ten (10) calendar days of the Sponsor-Investigator's knowledge of any other initial and follow-up SAEs
- Pregnancy Monitoring Forms shall be forwarded within seven (7) days of Sponsor-Investigator awareness of the pregnancy

BI Unique Entry Point:

Boehringer Ingelheim Pharmaceuticals, Inc
[name]
[name]
[contact]
E-mail: [contact].

With receipt of follow-up information, all remaining fields on the SAE form are to be completed or updated.

The investigator does not need to actively monitor the study subjects for adverse events once the clinical trial has ended. However, if the investigator becomes aware of an SAE(s) or AESI(s) that occurred after the adverse event reporting period as defined in Section 11.4.1 (including any protocol specified follow-up period/Residual effect period), it should be reported to BI if the investigator considers it as relevant to the BI study drug.

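### The Study Calendar schedules no adverse-event contact at the close of the 30-day post-dose window, so an early End of Treatment visit leaves the rest of that window without scheduled ascertainment

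*Combined protocol and SAP*

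**What the plan says.** Section 11.4.1 sets the collection windows. For AEs it is "All adverse events from the time of study treatment initiation until 30 days after last dose of study drug". For SAEs the start is earlier but the end is the same: "SAEs will be captured from the time of signing of the informed consent through 30 days after the date of the last study drug administration". AESIs have no separate window. Section 11.4.3, in dealing with "SAE(s) or AESI(s) that occurred after the adverse event reporting period as defined in Section 11.4.1", treats the Section 11.4.1 period as theirs too.

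Section 11.4.1 adds that the 30 days still apply when the subject has come off treatment and begun another anti-cancer therapy. The treating investigator remains responsible for follow-up even if the subject has moved or left that investigator's care.

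In the Study Calendar (Section 6) the AE evaluation row is marked at screening, runs as ongoing during treatment, and is marked once more at End of Treatment, a visit due "Within 30 days of last drug dose". The row is blank under Follow-up, where contact is "Every 6 months until death , LTF, or completion of long- term follow-up" and covers survival status, first subsequent therapy and, for some subjects, imaging. The blood count and metabolic panel are also last scheduled at End of Treatment.

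Section 5.5 has two relevant paragraphs. The one on AE evaluation requires all events to be monitored continuously under Section 11, whatever their grade or cause. The one on subsequent therapy says that after the End of Treatment visit "they will be followed until all treatment-related toxicities have resolved, returned to baseline, stabilized, or are deemed irreversible".

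**The concern.** The collection window and the visit schedule do not end together. The calendar wording bounds the End of Treatment visit from above only, so a visit in the first days after the last dose satisfies it. After that visit no call, clinic visit or laboratory test is scheduled to find new events before the window closes.

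Safety and toxicity are a secondary objective (Section 1.2), and Section 13.3.5 will report incidence rates of treatment-emergent AEs and SAEs. This is a single-arm trial of at most 39 treated subjects, so there is no control arm subject to the same ascertainment, and a few missed events would visibly move a rate. The report could describe a 30-day window that was systematically ascertained for only part of its length, with that part varying between subjects. Events found only by asking the subject or by a blood test are the most exposed. The two liver-enzyme AESIs in Section 11.2 are examples, because their last scheduled test is also at End of Treatment.

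**Working it through.** The plan states no figure to reproduce, and the point does not depend on sample size, power or alpha. The check compares the two schedules and then does simple day arithmetic.

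**Step 1. What is scheduled after the last dose.**

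| Source | What it provides | Does it elicit new events up to day 30? |
|---|---|---|
| Section 6, End of Treatment column | AE evaluation, blood count, metabolic panel, on any day up to 30 | Only up to the visit day |
| Section 6, Follow-up column | Six-monthly contact; no AE evaluation | No |
| Section 6, note f | Imaging every 8 weeks (± 2), best effort, not for those who stop for progression | No; no AE evaluation attached |
| Section 5.5, subsequent therapy | Follow-up of treatment-related toxicities to resolution or stability | No dates or method; directed at known toxicities |
| Section 5.5, AE evaluation | Ongoing monitoring of all events | A duty, with no post-treatment contact named |
| Section 11.4.1 | Investigator responsible through the full period | A duty, with no contact named |

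Section 5.5 also mentions a safety monitoring period, but no contact marks its end.

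**Step 2. Days left after the last scheduled assessment.** Let d be the day of the End of Treatment visit after the last dose, from 0 to 30. Days remaining = 30 − d; share of the window = (30 − d)/30. The visit days are assumed, because the documents give no distribution.

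| Visit day d | Days remaining | Share of window |
|---|---|---|
| 0 | 30 | 100% |
| 7 | 23 | 77% |
| 14 | 16 | 53% |
| 21 | 9 | 30% |
| 28 | 2 | 7% |
| 30 | 0 | 0% |

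A visit on any of days 0 to 15, which is 16 of the 31 permitted days, leaves at least half of the window. If visit days were spread evenly over 0 to 30 (an assumption), the average would be 15 days.

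**Step 3. Days are not events.** If new onsets become rarer after stopping, the share arising after the visit is smaller than the share of days. As an illustration, suppose the onset rate halves every h days, and let k = ln 2 / h. The share of the window's onsets arising after day d is (e^(−kd) − e^(−30k)) / (1 − e^(−30k)).

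| Visit day | Constant rate | h = 14 days | h = 7 days |
|---|---|---|---|
| 7 | 77% | 62% | 47% |
| 14 | 53% | 35% | 21% |
| 21 | 30% | 16% | 8% |

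These are shares of events that arise after the visit. They are not shares missed, since some would reach the investigator without a scheduled contact. Neither the onset pattern nor the unscheduled detection rate is in the documents.

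**Step 4. After the fix.** With an AE contact at or just after day 30, the part of the window after the last scheduled assessment is 0 of 30 days.

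**The case against.** The strongest reply is that the protocol already covers this period. Section 11.4.1 keeps the investigator responsible for all 30 days and expressly covers subjects who start other therapy or leave that investigator's care. Section 5.5 requires monitoring of all events regardless of attribution. This stands. A reader might infer from the calendar that a site may close AE collection a few days after the last dose, but the documents do not support that: such a site would breach Section 11.4.1. What the reply does not supply is a scheduled contact through which the duty is met.

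A second reply concerns size. Section 3 lists perforation, bleeding, thromboembolism and liver-enzyme rises as risks of therapy without saying that they arise late. Section 2.2.1 gives a terminal half-life of 7 to 19 hours, and Section 2.2.2 describes enzyme rises as reversible after stopping. This also stands, so the plan gives no ground for saying that events will be under-counted, only that they could be. Nor is every subject affected: a visit at or near day 30 leaves little or no gap.

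A reader might also infer that a long interruption before the decision to stop creates the same gap, because Section 5.1 dates discontinuation by the investigator's decision and Section 8.2 contemplates interruptions beyond 14 days. It does not. If the decision comes after day 30, the End of Treatment evaluation falls after the window and can cover all of it. At most, that is a difficulty in meeting the visit date.

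**Conclusion.** The mismatch is real, and its reach is limited. The calendar permits an End of Treatment visit well before day 30 and schedules nothing afterwards to elicit new AEs, SAEs or AESIs, while Section 11.4.1 collects them to day 30. The unscheduled part is 30 − d days, anywhere from 0 to 30 depending on visit dates that the documents do not give. It is a permitted gap, not a certain one.

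The consequence is possible under-counting of late events in the safety summaries, by an amount that cannot be computed from the documents. The percentages above describe days, or onsets under stated assumptions, and should not be read as the fraction of events lost. The primary endpoint, the two-stage rule and the efficacy analyses are unaffected. The change is worth making because it is cheap and would make the stated 30-day window one that is systematically ascertained.

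**What to change.** Reconcile Section 6 with Section 11.4.1 by one of two changes, with matching wording in Section 5.5:

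- Set the End of Treatment safety assessment at about day 30 after the last dose (for example day 30, +7 days), replacing the open-ended timing in the column header.
- Keep the present visit timing and add a day-30 telephone contact covering AEs, SAEs and AESIs for any subject whose End of Treatment visit is earlier.

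The second option follows existing practice. Notes n and o to the calendar already accept telephone contact for the Day 8 and Day 15 blood-pressure results and attach an AE evaluation to those contacts.

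The cost is calendar and Section 5.5 wording plus one call per subject seen early, so at most 39 calls. Reported AE counts may rise slightly. A call will not detect silent laboratory changes. If the liver-enzyme AESIs are to be ascertained to day 30, the first option does this, provided the metabolic panel stays with the assessment.
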